**Table 4      Planned Laboratory Evaluations**

Haematology	Serum Chemistry:
Haematocrit	Albumin
Haemoglobin	Alkaline phosphatase
Mean corpuscular haemoglobin	Alanine aminotransferase (ALT)
Mean corpuscular haemoglobin concentration	Amylase
Mean corpuscular volume	Aspartate aminotransferase (AST)
Platelet count	Blood urea nitrogen
Red blood cell count	Calcium
White blood cell count with differential (absolute count)	Carbon dioxide
	Chloride
Urinalysis:	Creatinine
Appearance	Creatine kinase
Bilirubin	Gamma-glutamyl transferase
Colour	Glucose (non-fasting)
Glucose	Lactate dehydrogenase
Ketones	Lipase
Leucocyte esterase	Magnesium
Microscopic examination of sediment a	Phosphorus
Nitrite	Potassium
Occult blood	Sodium
pH	Total bilirubin
Protein	Direct bilirubin
Specific gravity	Total cholesterol
Urobilinogen	Total protein
	Triglycerides
Pregnancy:	Urine Drug Screen (UDS):
Serum hCG	Opioids
Urine hCG	Cocaine
Molecular	Amphetamines
PCR for COVID-19	Cannabinoids
	Barbiturates
Screening Only:	Benzodiazepines
FSH (as needed in post-menopausal females only)	Methamphetamine
Haemoglobin A1c	Phencyclidine
Hepatitis B surface Antigen	Ethanol
Hepatitis C Antibody	In addition to the above, for Part III:
HIV-1 and -2 antibodies	Fentanyl
Prothrombin Time with INR	Oxycodone
PTT	

Anti-HIV = human immunodeficiency virus antibodies; hCG = human chorionic gonadotropin; INR = international normalized ratio; and PTT = partial thromboplastin time.

a Microscopic examination of sediment will be performed only if the results of the urinalysis evaluation are positive (microscopic examination may include but is not limited to White Blood Cell count, Red Blood Cell count, casts and crystals).

### 5.5.3.2. Vital Signs

Vital signs (systolic and diastolic blood pressure, heart rate, respiratory rate, temperature) will be summarized as observed values and changes from baseline by analysis visit and time point. Vital signs during the run-in period will be summarized separately.

### 5.5.3.3. Electrocardiogram (ECG) Data

Numeric 12-lead ECG parameters [heart rate, PR interval, QRS duration, QT interval, Fridericia's corrected QT interval (QTcF)] will be summarized as observed values and changes from baseline by analysis visit and time point. ECG interpretation (normal, abnormal not clinically significant, abnormal clinically significant) will be summarized by visit and time point as shifts from baseline.

### 5.5.3.4. Columbia-Suicide Severity Rating Scale (C-SSRS)

The composite endpoints Suicidal Ideation and Suicidal Behavior will be derived from the following 10 binary C-SSRS questions, reordered from the actual scale to facilitate the derivation:

Question 1	Wish to be Dead
Question 2	Non-specific Active Suicidal Thoughts
Question 3	Active Suicidal Ideation with Any Methods (Not Plan) without Intent to Act
Question 4	Active Suicidal Ideation with Some Intent to Act, without Specific Plan
Question 5	Active Suicidal Ideation with Specific Plan and Intent
Question 6	Preparatory Acts or Behavior
Question 7	Aborted Attempt
Question 8	Interrupted Attempt
Question 9	Actual Attempt (non-fatal)
Question 10	Completed Suicide

Suicidal Ideation is derived as “yes” if any of Question 1-5 has a “yes” response. Suicidal Behavior is derived as “yes” if any of Question 6-10 has a “yes” response. If there are zero “yes” responses and at least one question has a missing response, the derived composite will be missing. Suicidal Ideation and Suicidal Behavior will be summarized as categorical variables by analysis visit.

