3.3.1.1 Safety Assessments

Part I, Part II and Part III:

The following clinical safety parameters will be assessed for means, trends and/or changes from baseline. Clinically significant findings for the following clinical safety assessments will be reported as adverse events:

- laboratory results
- electrocardiogram (ECG) findings
- vital sign measures
- physical examination
- Columbia-Suicide Severity Rating Scale (C-SSRS)

•

Confidential Page 27 of 108

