5.3 Exclusion Criteria

Subjects must not meet any of the following criteria:

1. Have a medical history of clinically significant neurological, cardiovascular, renal, hepatic, chronic respiratory or gastrointestinal disease, or psychiatric disorder as judged by an Investigator.

Confidential Page 30 of 108

- 2. Have clinically significant abnormal biochemistry, haematology or urinalysis results as judged by an Investigator or medically responsible physician. (Refer to additional laboratory exclusion criteria for Part III subjects in Exclusion 28).
- 3. Have a history of narcolepsy or other significant sleep disorders.
- 4. Have disorders that may interfere with drug absorption, distribution, metabolism and excretion (ADME) processes.
- 5. Positive test results for HIV-1/HIV-2 Antibodies, Hepatitis B surface Antigen (HBsAg) or Hepatitis C Antibody (HCVAb).
- 6. Serious cardiac illness or other cardiac assessments including, but not limited to:
 - a. Uncontrolled arrhythmias.
 - b. History of congestive heart failure (CHF).
 - c. Myocardial infarction <6 months from receipt of first dose of IMP
 - d. Uncontrolled symptomatic angina
 - e. QTcF >450 msec for males and >470 msec for females or history of prolonged QT syndrome.
- 7. Current active hepatic or biliary disease, including subjects with cholecystectomy <90 days prior to Screening.
- 8. Concurrent treatment or treatment with an investigational drug, or participation in any other clinical study within 30 days prior to the signing the informed consent form.
- 9. History of suicidal ideation within 30 days prior to providing written informed consent as evidenced by answering "yes' to questions 4 or 5 on the suicidal ideation portion of the C-SSRS completed at the Screening Visit or history of a suicide attempt (per the C-SSRS) in the 6 months prior to informed consent.
- 10. Pregnant or lactating females.
- 11. Any consumption of food or drink containing poppy seeds, grapefruit or Seville oranges within 7 days prior to the IMP administration.
- 12. Blood donation of greater than 500 mL within 56 days or plasma donation within 7 days of screening; clinically significant anaemia or low haemoglobin (<11 g/dL for females, <12 g/dL for males).
- 13. Treatment with any known drugs that are moderate or strong inhibitors/inducers of cytochrome P450 (CYP) 3A4 within 30 days prior to first dose of IMP.
- 14. Known allergy or hypersensitivity to IMP or its excipients.

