6.5.2 Suicidal Ideation and Behaviour

Please refer to Section 8.8 for prospective assessment of suicidal ideation and behaviour. If a subject exhibits suicidal behaviour or active suicidal ideation with intent during the study, the Investigator should discontinue the subject and provide the appropriate treatment.

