14.9.6 Columbia-Suicide Severity Rating Scale

The composite endpoints Suicidal Ideation and Suicidal Behaviour will be derived from the following 10 binary C-SSRS questions, reordered from the actual scale to facilitate the derivation:

Question 1	Wish to be Dead	
Question 2	Non-specific Active Suicidal Thoughts	
Question 3	Active Suicidal Ideation with Any Methods (Not Plan) without Intent to Act	
Question 4	Active Suicidal Ideation with Some Intent to Act, without Specific Plan	
Question 5	Active Suicidal Ideation with Specific Plan and Intent	
Question 6	Preparatory Acts or Behaviour	
Question 7	Aborted Attempt	
Question 8	Interrupted Attempt	
Question 9	Actual Attempt (non-fatal)	
Question 10	Completed Suicide	

Suicidal Ideation is derived as "yes" if any of Question 1-5 has a "yes" response. Suicidal Behaviour is derived as "yes" if any of Question 6-10 has a "yes" response. If there are zero "yes" responses and at least one question has a missing response, the derived composite will be missing. Suicidal Ideation and Suicidal Behaviour will be summarized as a categorical variable by analysis visit.

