22.3 APPENDIX 3 – Schedule of Events Part III

22.3.1 Part III - Screening and SUBOXONE SL Film Run-In

	Sousoning		SUBC	OXONE S		l Film	
Evaluation	Screening		Induction (3 days)		Dos	e-Adjust (3 days)	
	Days -35 to -7	Day -6	Day -5	Day -4	Day -3	Day -2	Day -1 ⁷
Informed Consent	X						
Inclusion/Exclusion Criteria	X						
COVID-19 PCR Test		X					
Admission to Clinical Unit ¹		X					
Demographics (Includes height, weight and BMI)	X						
Medical History	X						
Physical Examination ²	X						
Urine Drug Screen	X	X					
Alcohol test	X	X					
Serum Pregnancy Test	X						
Urine Pregnancy Test		X					
Urinalysis	X						
Clinical Laboratory Assessments (Chemistry and Haematology)	X	X^3					
Serology (HIV, Hepatitis B and C)	X						
Coagulation Panel (PT/INR)	X						
FSH (post-menopausal females only)	X						
Vital Signs	X	X ⁴	X ⁴	X^4	X ⁴	X ⁴	X^4
12-Lead Electrocardiogram	X						
SUBOXONE SL film Administration ⁵		X	X	X	X	X	X
AE Assessment		X	X	X	X	X	X

Page 87 of 108

	S	SUBOXONE Sublingual Film (In clinical unit)										
Evaluation	Screening	1	nductio (3 days		Dos	e-Adjust (3 days)						
	Days -35 to -7	Day -6	Day -5	Day -4	Day -3	Day -2	Day -1 ⁷					
Concomitant Medication Assessment		X	X	X	X	X	X					
C-SSRS ⁶	X											

- 1: Confirm Check-In Criteria (defined in Section 5.4) prior to admission to the unit.
- 2: A full physical examination will be completed at Screening. For male participants, a testicular exam will be performed.
- 3: Clinical Laboratory Assessments are conducted pre-dose (-1 hr).
- 4: To be conducted pre-dose (-30 mins), and then at 2 hours (± 30 mins)
- 5: Administer per the USPI.
- 6: Lifetime assessment to be completed during screening.
- 7: Day -1 procedures on this table are to be conducted prior to Run-In Assessment criteria on next table

Confidential Page 88 of 108

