8:12-lead ECG tracing is to be obtained at admission, and on Days 2, 3, 5, 7, 9, 11 and 13 at pre-dose (-1 hr), 2 hrs post-dose (±30 min). All timepoints are relative to the AM dose. Triplicate tracings will be obtained at least 1 minute apart on pre-dose Day 1 and as needed to assess stopping criteria.

13: Baseline assessment to occur at Day -1, all remaining assessments will be 'Since Last Visit' CSSR-S.

Confidential Page 90 of 108

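### The C-SSRS is summarized only as two yes/no composites by visit, so a rise within ideation levels 1-3 is never counted, and a pre-dose 'yes' or missing form leaves a later 'yes' unclassifiable as new

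*SAP*

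**What the plan says.** The two documents agree on the output. SAP 5.5.3.4 says that "Suicidal Ideation and Suicidal Behavior will be summarized as categorical variables by analysis visit", and Protocol 14.9.6 says that "Suicidal Ideation and Suicidal Behaviour will be summarized as a categorical variable by analysis visit". In both, any 'yes' among Questions 1-5 makes ideation 'yes', and any 'yes' among Questions 6-10 makes behaviour 'yes'. With no 'yes' and at least one unanswered item, the composite is missing.

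The surrounding provisions that matter are these:

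- Protocol 3.3.1.1 lists the C-SSRS with laboratory results, ECG, vital signs and physical examination and says: "The following clinical safety parameters will be assessed for means, trends and/or changes from baseline". It adds: "Clinically significant findings for the following clinical safety assessments will be reported as adverse events".
- Protocol 6.5.2 tells the investigator to discontinue the subject in this case: "If a subject exhibits suicidal behaviour or active suicidal ideation with intent during the study".
- Exclusion 9 removes candidates with recent ideation at the two highest levels or a recent attempt, by reference "to questions 4 or 5 on the suicidal ideation portion of the C-SSRS completed at the Screening Visit or history of a suicide attempt".
- On the forms, Protocol 22.3.1 says "Lifetime assessment to be completed during screening" and Protocol 22.3.2 says "Baseline assessment to occur at Day -1, all remaining assessments will be 'Since Last Visit' CSSR-S".
- SAP 5.1.5 defines baseline as the last value before the first IMP dose. SAP 5.5.3.4 makes no use of it.
- SAP 6.3 (Appendix 3) keeps only the most recent non-missing assessment when a visit has several.

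**The concern.** The C-SSRS is a graded scale, and Protocol 8.8 gives the drug's CNS activity as the reason for using it. The natural safety question is how many subjects had ideation or behaviour that was new, or worse, after INDV-2000 started. Two yes/no rows by visit do not answer it in two situations. A subject at level 1 before dosing who stays at level 1 and a subject who moves from level 1 to level 3 produce the same string of 'yes'. And where a pre-dose cell is 'yes' or missing, the marginal counts do not show whether a later 'yes' is the same person.

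The plan treats comparable measures differently. ECG interpretation is also categorical and gets shifts from baseline (SAP 5.5.3.3). Adverse events get a maximum-severity table (SAP 5.5.2). At stake is the readability of one safety summary; no error rate or sample size is affected.

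**Working it through.** The plan states no figure on this point, so there is none to reproduce. The check is a form count, a bounds calculation and a comparison of sections.

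**Forms per subject (Protocol 22.3.1 and 22.3.2).** There is one Lifetime form at screening, then forms on Days -1, 2, 4, 6, 8, 10, 12, 14 and 21: 1 + 9 = 10. INDV-2000 starts on Day 3, so two of the nine precede it (Days -1 and 2) and seven follow it (Days 4 to 21). The within-subject comparison is already in the data.

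**Can a pre-dose 'yes' occur?** Exclusion 9 covers Question 4 or 5 ideation within 30 days before consent, or an attempt within 6 months. Levels 1-3 do not exclude under that criterion, although exclusions 1 and 15 may remove some such subjects.

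**What the counts determine.** Let N = 16, m the counts of 'yes' at the two pre-dose visits and n the counts at the seven post-dose visits.

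- Distinct pre-dose subjects P lie in [max m, min(N, sum m)].
- Distinct post-dose subjects Q lie in [max n, min(N, sum n)].
- New subjects lie in [max(0, Qmin - Pmax), min(Qmax, N - Pmin)].

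With complete data:

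| Pre-dose 'yes' | Post-dose 'yes' | Distinct post-dose | New |
|---|---|---|---|
| none | 2, at one visit | 2 | 2 |
| 1, on Day -1 | 1, at one visit | 1 | 0 or 1 |
| 1, on Day -1 | 1 at each of two visits | 1 or 2 | 0, 1 or 2 |
| 2, on Day -1 | 2, at one visit | 2 | 0, 1 or 2 |

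For the third row: Q is in [1, 2] and P = 1, so new lies in [max(0, 1 - 1), min(2, 15)] = [0, 2]. The first row shows the limit of the problem: with all pre-dose cells zero and complete, every post-dose 'yes' is new.

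**Which rises the composite hides.** Code ideation 0 (none) to 5. There are 15 possible upward moves. Five start from 0 and change the composite; ten start from 1 or higher and do not. Of those ten, seven end at level 4 or 5, which involves intent and falls under Protocol 6.5.2. The other three (1 to 2, 1 to 3, 2 to 3) have no such route.

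**How often?** The documents give no ideation rate. Purely as an assumption, a pre-dose rate p gives a chance 1 - (1 - p)^16 of at least one pre-dose 'yes': 28% at p = 2%, 56% at 5%, 81% at 10% and 97% at 20%. The range is too wide to support any conclusion.

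**Side by side.** Of the five parameters legible in Protocol 3.3.1.1, laboratory data, vital signs and ECG get change or shift summaries (SAP 5.5.3.1 to 5.5.3.3). Physical examination goes to adverse events only (Protocol 14.9.5). The C-SSRS gets by-visit composites only.

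**Repeat forms.** Under SAP 6.3, a 'yes' followed by a 'no' at the same visit drops out of the summary.

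**The case against.** The best defence is that other routes already catch what matters. Protocol 10 counts new or exacerbated conditions as adverse events, and Protocol 10.1.2 records a pre-existing event that worsens after study drug as a new event. These enter the treatment-emergent tables, including the one by maximum severity. Individual data are listed (Protocol 14.1), and with at most 16 subjects a reader can work from the listings. This largely stands. It does not close the gap, because Protocol 10.1 makes a scale finding an adverse event only if it needs intervention or the investigator judges it clinically significant. Ideation below intent that meets neither test appears in no summary as new or worse.

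The second defence is that the absence cannot be confirmed. SAP 6.4.3.1, a safety derivation, is redacted, and table shells are in a separate document (SAP 5.1.3). This stands as a limit: the point concerns only the unredacted text.

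A reader might infer more than the documents support:

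- *That the SAP breaches Protocol 3.3.1.1.* It does not. The 'and/or' wording is met by counts that show a trend over visits, and physical examination has no change summary either.
- *That any non-zero post-dose count is ambiguous.* It is not; the new-versus-pre-existing ambiguity needs a pre-dose 'yes' or missing form.
- *That ten of fifteen worsening patterns would go unnoticed.* Seven of them reach intent and should lead to discontinuation.
- *That uncertainty over distinct subjects is a C-SSRS defect.* Other visit-based tables in the SAP share it.

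**Conclusion.** The point holds as an optional, cheap improvement of low materiality. As far as the unredacted text shows, no summary counts a rise within ideation levels 1-3, and a post-dose 'yes' cannot be classed from the table once a pre-dose cell is 'yes' or missing. What goes unsummarized is ideation below intent that needs no intervention and is not judged clinically significant, in a descriptive study of at most 16 subjects whose listings allow it to be recovered by hand. If every post-dose cell is zero and complete, nothing is lost.

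This rests on two assumptions: that neither the redacted derivation nor the table shells already contain a shift or a new/worsened definition, and that investigators apply the adverse event and discontinuation rules as written. If the first is wrong, a sentence in SAP 5.5.3.4 saying so would settle the matter.

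**What to change.** Keep the by-visit table and add the following to SAP 5.5.3.4:

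1. One Safety Population shift table of worst category before first INDV-2000 (Day -1, Day 2 and unscheduled forms) against worst category after it. Use the categories none / ideation 1-3 / ideation 4-5 / behaviour, with missing shown separately, and use all assessments instead of only the most recent per visit.
2. Any-time counts and percentages of subjects with new ideation, worsened ideation (a higher maximum level on 1-5, so that a rise within levels 1-3 is counted) and new behaviour.
3. The Lifetime screening form shown separately. Before the Day -1 form enters 'worst before', confirm that its recall period is not lifetime, since a long recall would hide worsening.
4. A footnote that the Day 4 form looks back to Day 2 and so can cover time before the first dose on Day 3, with a flag for subjects whose only post-dose 'yes' is on that form.
5. An entry in SAP Appendix 2 recording the addition and stating that this table uses the worst pre-dose value in place of the last-value baseline of SAP 5.1.5.

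The cost is one table and a few lines of text, built from items already collected, with no change to study conduct. The downside is one more table that may contain only zeros.

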## 5.6. Other Analyses

### 5.6.1. Demographic and Baseline Characteristics

Demographic and other baseline characteristics will be summarized separately for the run-in safety, safety, and PK populations, if different. Parameters to be summarized will be age, sex, race, ethnicity, fertility status, height/weight/body mass index, and substance use (alcohol, nicotine, xanthine/caffeine) status (never/current/former). Listings will include all subjects, including screen failures and run-in failures.

---

### **5.6.2. Medical History**

Relevant medical history will be coded using MedDRA (refer to the Data Management Plan) and will be listed for the run-in safety population.

### **5.6.3. Prior and Concomitant Medications and Therapies**

Medications and therapies will be collected from screening through EOS and will be coded using Anatomical Therapeutic Chemical (ATC) classification codes via the World Health Organization Drug Dictionary (WHO-DD). Additional details of the coding process, including the current version of the dictionary, are described in the Data Management Plan. Prior medications and therapies will be medications/therapies that ended before first administration of study drug or were taken by subjects who did not take study drug. Therapies and medications that were started or were ongoing during run-in will be considered run-in therapies and medications. Therapies and medications that were started or were ongoing post run-in will be considered concomitant therapies and medications. A therapy or medication can be both run-in and concomitant. Therapies/medications will be assigned to study treatments based on start dates and times of treatments and start and end dates and times of therapies/medications.

Prior concomitant medications and therapies will be summarized for all subjects. Run-in medications and therapies will be summarized for the run-in safety population. Concomitant medications and therapies will be summarized for the safety population. The summary of incidence (number and percentage of subjects reporting the medication/therapy at least once) will be sorted alphabetically by therapeutic class (ATC level 2) and standardized medication/therapy name.

See Section [6.6.4 \(Appendix 6\)](#) for details on handling missing information on medications and therapies.

### **5.6.4. Protocol Deviations**

Protocol deviations will be identified and documented prior to database lock and will be summarized by category (eg, prohibited medication, out-of-window assessment) and type (eg, major, minor), per the Protocol Deviation Plan for the study, for the run-in safety population. Deviations that occur in subjects who were not dosed with study drug, if any, will be summarized separately. All protocol deviations will be listed.

### **5.7. Interim Analyses**

Not applicable.

## **6. SUPPORTING DOCUMENTATION**

[figure not shown]
## 6.1. Appendix 1: List of Abbreviations

Abbreviation	Term
ADaM	Analysis Data Model
AE	adverse event
ATC	Anatomic Therapeutic Chemical
BLQ	below limit of quantitation
C-SSRS	Columbia-Suicide Severity Rating Scale
CRF	Case Report Form
CSR	clinical study report
ECG	electrocardiogram
EOS	end of study
h	hours
IMP	investigational medicinal product
MedDRA	Medical Dictionary for Regulatory Activities
mm	millimeter
OUD	opioid use disorder
PK	pharmacokinetic
PT	Preferred Term
QTcF	Fridericia's corrected QT interval
SAE	serious adverse event
SAP	statistical analysis plan
SD	standard deviation
SDTM	Study Data Tabulation Model
SL	sublingual
SOC	System Organ Class
TEAE	treatment-emergent adverse event
TESAE	treatment-emergent serious adverse event
TFLs	tables, figures, and listings
WHO-DD	World Health Organization Drug Dictionary

## **6.2. Appendix 2: Changes to Protocol-Planned Analyses**

The following are changes from the protocol that are in the SAP:

Protocol:	SAP:
	Added Screened analysis population.
	Added Enrolled analysis population.

[figure not shown]

## **6.3. Appendix 3: Definition and Use of Visit Windows in Reporting**

[figure not shown]
No windowing will be used for summaries. Analysis visits will be visits denoted in the Case Report Form (CRF). If a subject has more than 1 assessment for a given visit, the most recent non-missing assessment will be used for summaries.

[figure not shown]
## **6.4. Appendix 4: Endpoint Derivations**

[figure not shown]
### **6.4.1. Pharmacokinetic Endpoints**

### **6.4.2. Pharmacodynamic Endpoints**

#### **6.4.3. Safety Endpoints**

[figure not shown]
